6.4 PROTOCOL VIOLATIONS

Protocol violations will be summarised in the clinical study report (CSR). This summary will include the number and percent of subjects with each violation type. Major violations in this study may be those that are related to:

- Informed consent deviation
- Inclusion/Exclusion criteria, if such protocol violation is likely to impact one of the two primary endpoints
- Participant not complying with trial protocol

The main reason for assessing the incidence of major violations during the study is to determine which patients are in the per-protocol population (the per-protocol population excludes "major" violations). Prior to database lock, all protocol violations will be reviewed and patients who have had major violations will be noted and excluded from the per-protocol population.

6.5 MULTIPLE ENDPOINT ADJUSTMENT

There will be no adjustment for the multiple secondary endpoints. All secondary outcomes will be considered exploratory.

7 DEMOGRAPHICS AND OTHER BASELINE CHARACTERISTICS

7.1 DEMOGRAPHICS

Demographics will be summarised by randomised treatment groups. There will be no formal statistical comparisons between treatment groups on demographic variables. We will present variables with a normal distribution as mean (standard deviation). Variables with a skewed distribution will be summarised as median (interquartile range). Categorical variables will be presented as numbers (percentages).

7.2 BASELINE MEDICAL HISTORY

The medical history of all ITT and the safety analysis population subjects will be summarised in a table by treatment group. Specifically, the number and per cent of subjects who currently have the condition will be presented for each condition.

7.3 BASELINE LABORATORY MEASUREMENTS

A table presenting descriptive statistics (sample size, mean, standard deviation, median, min and max) of laboratory variables by treatment group at baseline will be provided for the ITT analysis set. If the baseline value is missing for a given variable and patient, the screening value will be used before calculating the descriptive statistics.

8 EFFICACY ANALYSES

8.1 PRIMARY OUTCOME

Number of ovulatory cycles

We will fit a GLM with the Poisson distributional family and a log link function. The Poisson model will be the primary analysis. Results will be presented as incidence rates and incidence rate ratios (95% confidence interval). Standard techniques will be employed to verify the model assumptions, which include residual analysis, overdispersion testing, and influence diagnostics. In case of substantial overdispersion, we may utilise a negative binomial model. As a sensitivity analysis, we will conduct a bootstrap t-test for independent samples. The analysis will include all participants who have complete follow-up data. We will use bias-corrected and accelerated (BCa) intervals via 10.000 replicates.

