3. STUDY DESIGN

In this prospective open-label RCT we propose to recruit 80 women with PCOS, obesity and oligo or amenorrhea from Imperial College Healthcare NHS Trust, University Hospitals Coventry & Warwickshire NHS Trust, two centres with tertiary obesity and reproductive endocrinology expertise, and the Hammersmith and Fulham GP Partnership.

They will be eligible for obesity surgery based on NICE CG189. Patients will be randomised at a ratio of 1:1, stratified by BMI and trial site to:

- Standard medical care (n=40): combination of an intensive lifestyle intervention ± pharmacotherapy or
- Obesity surgery (n=40): standard laparoscopic VSG.

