7. STATISTICS AND DATA ANALYSIS

Justification of sample size

Based on the available data on the effect size of lifestyle interventions [5, 19] and obesity surgery [10] on ovulation we estimated that women in the standard medical care group will have a mean of 7 and women in the obesity surgery group a mean of 10 ovulatory cycles in the 12 month follow-up period. With a standard deviation of 3.3 around both means, we will need 33 women in each group to have a 95% power to detect statistically significant differences between the groups at α of 0.05. We will recruit 40 patients in each group to account for a 15-20% drop-out rate based on rates in similar trials we have conducted in this field (LIPOS UTN: U1111-1126-3292 and DOMINO ISRCTN76278694).

Statistical analysis plan

Analysis of the data will only take place after completion of the trial having written a statistical analysis plan and use the intention to treat principle. Data will be summarised using descriptive statistics. Differences between treatment groups will be compared using ANCOVAs and/or chi-square tests adjusting for the randomisation stratification variables and baseline value of the tested parameter.

8. **REGULATORY ISSUES**

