Appendix 1. Summary of investigations and assessments

Assessment													
	Baseline	1 mo	2 mo	3 mo	4 mo	5 mo	6 mo	7 mo	8 mo	9 mo	10 months	11 months	12 months
Number of reported menses	х	х	х	х	х	х	х	х	х	х	Х	Х	х
Body weight	х	х	х	х	х	х	х	х	х	х	х	х	х
waist circumference													
body composition													
Plasma lipids	х						х						х
HbA1c													
liver function tests													
Blood pressure	х						х						х
Reproductive hormones	х	х	х	х	х	х	х	х	х	х	Х	Х	х
Anti-mullerian hormone	х						х						х
Urine pregnancy test	х	х	х	х	х	х	х	х	х	х	х	х	х
Progesterone	Weekly throughout trial												
Questionnaires	х						х						х
Hirsutism and alopecia	х						х						х
indices													
Number of medications	х	х	х	х	х	х	х	х	х	х	х	х	х
Adverse events	х	х	х	х	х	х	х	х	х	х	х	х	х
Energy expenditure	х						х						
Sleep studies	х						х						
Endometrial biopsy	х						х						
Adipose tissue biopsy	х						х						
Oral glucose tolerance test	х						х						х

Appendix 2

Sub-studies

All participants will be given the opportunity to take part in one or more state-of-the-art studies that will investigate the physiological mechanisms underpinning the clinical impact of the two treatments. These mechanistic studies will be optional and focus on:

- Energy expenditure and sleep-disordered breathing
- Endometrial clonal activity
- Adipose tissue biology
- Functional MRI

Energy expenditure and sleep-disordered breathing

All patients will be offered an optional metabolic study at the Human Metabolic Research Unit (HMRU) for body composition, energy expenditure and sleep study. This metabolic study will take place at baseline and 6 months post-intervention follow-up.

Each HMRU study will commence at 8am with measurement of body composition in the BodPod, which provides an accurate measurement of body composition. Participants will have fasted overnight. Each participant will enter the metabolic chamber at 9:30am for a 24-hour metabolic study to measure energy expenditure profile in real time. Prior to entry into the chamber, each participant will be shown around the chamber by the HMRU nurse, for orientation purposes. Throughout their 24-hour stay within the calorimeters, subjects will be asked to collect their urine in specific containers provided by the research team. These will be collected 8-hourly and used for the assessment of substrate oxidation.

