GLM	Generalised linear model
CSR	Clinical study report
SAE	Serious Adverse Event
TEAE	Treatment emergent adverse event
AE	Adverse Event
SOC	System organs class
РТ	Preferred Term
CRF	Case Report Form

STUDY DESIGN

This is an open-label randomised-controlled clinical trial to investigate the safety and efficacy of obesity surgery vs medical care for women with polycystic ovary syndrome (PCOS), obesity and oligo- or amenorrhoea.

Patients will be randomised at a ratio of 1:1, stratified by body mass index (BMI) and trial site to:

- Medical care: a combination of lifestyle modification and pharmacotherapy or
- Obesity surgery: standard laparoscopic vertical sleeve gastrectomy (VSG).

Key Inclusion criteria

- Pre-menopausal women ≥ 18 years old
- BMI \ge 35 kg/m² with obesity-related complications
- Diagnosis of PCOS based on international evidence-based guidelines for the assessment and management of PCOS 2018

Key Exclusion criteria

- Type 1 or Type 2 diabetes mellitus
- Specific contraindications to obesity surgery
- Previous obesity surgery
- Inability to maintain adequate contraception
- Medications affecting reproductive function (e.g. oral steroids, hormonal contraceptives) at screening or 3 months previously.
- Other causes of anovulation (e.g. untreated hypothyroidism, adrenal or pituitary disorders)
- Current pregnancy or breastfeeding

Key outcomes

Reproductive

- Weekly serum progesterone
- Monthly profile of reproductive hormones
- Self-reported menses

Metabolic

- Oral glucose tolerance test measuring glucose and insulin secretion and sensitivity indices. This will take place pre-intervention, at 26 weeks and 52 weeks post-intervention.
- Monthly metabolic profile: fasting glucose, insulin, and HOMA-IR.

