6 GENERAL ISSUES FOR STATISTICAL ANALYSIS

6.1 ANALYSIS SOFTWARE AND GENERAL METHODS OF ANALYSIS

We will use SPSS (version 27, IL, USA) for all analyses. Two-sided P-values < 0.05 will be considered statistically significant.

- *Primary outcome:* Number of ovulatory cycles
 - The primary outcome was considered a Poisson distributed variable. Thus, we will fit a generalised linear model (GLM) with the Poisson distributional family and a log link function.
- Secondary efficacy outcomes:
 - Continuous outcomes: We will fit mixed-effects linear models (random intercept models). In the fixed-effects parts of the models, we will include group (1 = obesity surgery, 0 = medical care) and time as a continuous outcome. Number of reported menses within the 52-week follow-up period: We will use an identical approach compared to the primary outcome, namely a Poisson regression model via GLM and bootstrap Student's t test.
- *Secondary safety outcomes:* Safety outcomes will be evaluated via Fisher's exact tests at 52 weeks.

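### The protocol commits to adjusting for the randomisation strata and baseline value; the SAP carries neither into any model and gives no reason

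*SAP*

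**What the plan says.** Both documents describe stratified allocation. Protocol section 3: "Patients will be randomised at a ratio of 1:1, stratified by BMI and trial site to" the two arms. The study design section of the SAP: "Patients will be randomised at a ratio of 1:1, stratified by body mass index (BMI) and trial site to" the same arms. Neither gives the BMI cut-point used for stratification.

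Protocol section 7 plans ANCOVA and/or chi-square comparisons "adjusting for the randomisation stratification variables and baseline value of the tested parameter".

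The SAP's analyses are:

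- **Primary outcome (6.1, 8.1):** "We will fit a GLM with the Poisson distributional family and a log link function". No predictors are listed, not even treatment group.
- **Fallback (8.1):** "In case of substantial overdispersion, we may utilise a negative binomial model". Again no covariates.
- **Sensitivity analysis (8.1):** "As a sensitivity analysis, we will conduct a bootstrap t-test for independent samples". This is unadjusted by construction.
- **Reported menses (8.2):** the same approach as the primary outcome.
- **Other secondary efficacy outcomes (6.1, 8.2):** random-intercept models in which "we will include group (1 = obesity surgery, 0 = medical care) and time as a continuous outcome", with a treatment-by-time interaction if it improves fit.
- **Safety (section 9):** unstratified Fisher's exact tests.

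No stratification factor or baseline covariate appears in any of these, and the SAP does not explain the departure from the protocol.

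**The concern.** Stratified randomisation makes the arms alike on the stratification factors. If those factors predict outcome, the treatment estimate varies less between repetitions of the trial than an unstratified analysis assumes. An analysis that estimates its variance from the data and ignores the strata then reports intervals that are too wide and tests below their nominal level. Adjusting for the strata removes the mismatch, and the protocol said this would be done.

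There is also a question of pre-specification. SAP section 2.2.1 says the final analysis follows both the protocol and the SAP, so both govern and they disagree. Because the primary model lists no predictors, an adjusted or an unadjusted rate ratio could each be presented afterwards as the planned one. In an open-label trial this should be settled before analysis.

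**Working it through.** **1. The plan's own sample size.** Inputs from SAP section 4: means 7 and 10, SD 3.3, two-sided alpha 0.05, power 95%, 33 per arm. The standardised difference is 3/3.3 = 0.909. The normal approximation gives 32 per arm. The exact t-test calculation gives power 94.7% at 32 and 95.3% at 33. The stated 33 is therefore reproduced, and it is the answer for an unadjusted comparison of two means. Planned power does not rely on covariate adjustment.

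**2. Omitting strata when the variance is estimated from the data.** Let R² be the share of outcome variance explained by the strata. The documents give no value, so a range is shown. With strata balanced between arms:

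- adjusted residual SD = 3.3 × √(1 − R²)
- 95% interval half-width at 33 per arm = 1.96 × SD × √(2/33)
- actual type I error of the unadjusted test = 2 × [1 − Φ(1.96/√(1 − R²))]

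| R² | Half-width unadjusted | Half-width adjusted | Ratio | Type I error, unadjusted |
|---|---|---|---|---|
| 0 | 1.59 | 1.59 | 1.00 | 5.0% |
| 0.10 | 1.59 | 1.51 | 1.05 | 3.9% |
| 0.20 | 1.59 | 1.42 | 1.12 | 2.8% |
| 0.30 | 1.59 | 1.33 | 1.20 | 1.9% |

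**3. The plain Poisson model.** Its model-based variance is fixed by the counts. With 33 per arm, SE(log rate ratio) = √[1/(33 × 7) + 1/(33 × 10)] = 0.0858, and no stratum variance enters. The SAP's SD implies a variance-to-mean ratio of 3.3²/7 = 1.56 under medical care and 3.3²/10 = 1.09 under surgery. Using that SD, the SE is √[10.89/(33 × 49) + 10.89/(33 × 100)] = 0.1002, which is 1.17 times the model-based one. The 95% interval for a rate ratio of 10/7 is 1.21 to 1.69 with the model-based SE and 1.17 to 1.74 with the larger one.

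**4. Simulation.** 1,500 trials per scenario, 66 women, four balanced strata (two BMI levels by two sites, assumed), mean 7 in both arms, total SD 3.3. Entries are type I error; the Monte Carlo standard error at 5% is √(0.05 × 0.95/1500), about 0.6 percentage points.

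| Standard error | Strata in model | R² 0 | 0.10 | 0.20 | 0.30 |
|---|---|---|---|---|---|
| Model-based Poisson | no | 12.3% | 9.2% | 8.2% | 7.3% |
| Model-based Poisson | yes | 12.3% | 9.2% | 8.2% | 7.3% |
| Dispersion-scaled | no | 6.0% | 4.5% | 3.5% | 2.2% |
| Dispersion-scaled | yes | 5.9% | 5.4% | 5.3% | 5.1% |
| Robust (HC1) | no | 6.3% | 4.8% | 3.7% | 2.3% |
| Robust (HC1) | yes | 6.3% | 6.3% | 6.2% | 6.8% |

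Adding the strata changes nothing for the model-based Poisson test, which is too liberal either way. With dispersion scaling, omitting the strata becomes increasingly conservative as R² rises, and including them keeps the level near 5%. The negative binomial was not simulated; the same reasoning plausibly applies.

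**5. Baseline value.** The primary endpoint is counted only during follow-up (SAP 3.2.1), so it has no baseline value. The commitment applies to the secondary outcomes, most of which Protocol Appendix 1 schedules at baseline. The SAP does not say whether those baseline measurements are responses in the mixed models, covariates or neither.

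**The case against.** The strongest reply is that little is at risk. Randomisation protects against bias without adjustment, the sample size was set for an unadjusted comparison, every R² above is assumed, and at R² = 0 nothing is lost. The SAP's silence on Poisson predictors is also not a statement that the strata are excluded, since section 2.2.1 still points to the protocol. All of this stands, and it limits the point to efficiency, calibration and consistency between the documents. It does not explain the departure, and the predictor list for the mixed models is explicit.

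Three stronger readings are tempting, and the documents do not support them.

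- *That the omission makes the primary Poisson interval too wide.* With model-based standard errors, balanced strata leave that interval unchanged. At the SAP's own SD it is too narrow, because of overdispersion.
- *That the SAP drops a baseline value for the primary outcome, or ignores a strong predictor in baseline menses.* There is no baseline ovulation count to drop. Appendix 1 does mark "Number of reported menses" at baseline, but defines no look-back window, and Protocol section 6 has a bleed induced before that visit. All the women are oligo- or amenorrhoeic, which restricts its range. Neither document states how prognostic it is, and the protocol did not promise this covariate.
- *That the trial is underpowered without adjustment.* The 33 per arm is reproduced without it.

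**Conclusion.** The protocol and SAP disagree on adjustment, and the SAP should be amended or the departure justified. For analyses that estimate their variance from the data, the cost of omitting the strata is conservative and conditional: about 3.9% or 2.8% type I error, and intervals about 5% or 12% wider than needed, if the strata explain 10% or 20% of variance. These R² values are assumptions, and the figures also assume close balance of the strata between arms. For the mixed models they refer to a between-woman group comparison.

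For the plain Poisson model, naming the strata restores agreement with the protocol but does not alter the reported interval. Calibration there depends on handling the overdispersion implied by a variance-to-mean ratio of 1.56 at a mean of 7, which the SAP leaves to an optional fallback. This is a worthwhile correction, not a threat to the validity of the trial.

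**What to change.** - **Primary count model:** list group, BMI stratum as randomised (with its cut-point stated) and site. Use a dispersion-scaled or robust variance, or a negative binomial model, as the planned analysis. In the simulation, dispersion scaling with strata held its level better (5.1% to 5.9%) than HC1 (6.2% to 6.8%); if a robust variance is chosen, specify a small-sample correction.
- **Reported menses:** use the same terms and variance.
- **Mixed models:** add BMI stratum and site. Adjust for each outcome's own baseline value with only post-baseline visits as responses, or keep baseline as a response with a common baseline mean for the two arms. Do not do both, because that uses baseline twice.
- **Unadjusted model:** keep it as supportive.
- **Baseline menstrual frequency:** optional in the count models, and only if its look-back window is defined to exclude the induced bleed.

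If the sponsor prefers unadjusted analyses, the SAP should say so and give the reason.

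The cost is SAP wording and a few degrees of freedom. The strata are known from randomisation, so they need no new data.

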3.2.2 SECONDARY EFFICACY ENDPOINTS

For each secondary endpoint, temporal changes, mean levels and peak levels will be analysed as appropriate:

- Anthropometric measurements body composition, waist circumference, body weight
- Metabolic outcomes glycated plasma haemoglobin (HbA1c), plasma liver function tests, plasma lipid profile
- Arterial blood pressure
- Reproductive hormones serum luteinising hormone (LH), follicle-stimulating hormone (FSH), oestradiol, sex hormone binding globulin (SHBG), testosterone, free androgen index (FAI), dehydroepiandrosterone sulfate (DHEAS), androstenedione, Anti Mullerian hormone (AMH)
- Number of reported menses
- Glucose concentrations at the oral glucose tolerance test (OGTT)
- Hospital Anxiety and Depression Scale (HADS) score
- Multidimensional Health Profile: Health Functioning questionnaire score
- PCOS Health-Related Quality of Life score
- Modified Ferriam-Galwey hirsutism score
- Ludwig visual score
- Savin alopecia scale score
- Cardiff Acne Disability index
- Number of medications

4 Sample Size

Based on the available data on the effect size of lifestyle interventions[1] and obesity surgery[2] on ovulation we estimated that women in the standard medical care group will have a mean of 7 and women in the obesity surgery group a mean of 10 ovulatory cycles in the 52-week follow-up period. With a standard deviation of 3.3 around both means, we will need 33 women in each group to have a 95% power to detect statistically significant differences between the groups at α of 0.05. We will recruit 40 patients in each group to account for a 15-20% drop-out rate based on rates in similar trials we have conducted in this field (LIPOS UTN: U1111-1126-3292 and DOMINO ISRCTN76278694).

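### The Poisson primary analysis implies a smaller variance than the SD of 3.3 used to size the trial; if that SD is right, type I error is about 6–12%, and the SAP's remedy is optional and undefined

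*SAP*

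**What the plan says.** SAP section 4 (Sample Size) plans on an average of 7 ovulatory cycles with medical care; for the other arm it gives "women in the obesity surgery group a mean of 10 ovulatory cycles in the 52-week follow-up period". It adds "With a standard deviation of 3.3 around both means" and concludes that "we will need 33 women in each group to have a 95% power to detect statistically significant differences". Section 7 of the protocol gives the same figures.

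SAP 6.1 then states: "The primary outcome was considered a Poisson distributed variable". SAP 6.1 and 8.1 specify a generalised linear model with Poisson family and log link, and 8.1 names it as the primary analysis, reported as incidence rate ratios with 95% confidence intervals. Neither section says whether the standard error is model-based, scaled for dispersion or robust. The significance rule in 6.1 is "Two-sided P-values < 0.05 will be considered statistically significant".

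SAP 8.1 commits to checking the model, including a test for overdispersion, and to a bootstrap t-test with BCa intervals as a sensitivity analysis. On what happens if the check fails, it says: "In case of substantial overdispersion, we may utilise a negative binomial model".

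**The concern.** A Poisson count has variance equal to its mean, so the primary model does not estimate the spread of the data. It takes the spread from the fitted mean. The sample size section assumes a larger spread than that, mainly in the medical care arm. If the planning figure is closer to the truth, the primary p-value is too small and the primary interval too narrow.

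This is the trial's only confirmatory efficacy test, since SAP 6.5 treats all secondary outcomes as exploratory. SAP 8.2 uses the same approach for reported menses, so the problem carries over to that outcome.

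The remedy is also loose. The SAP names no dispersion test and no cut-off for what counts as substantial, and the switch is permitted rather than required. The analysis follows database lock in an open-label trial, so the choice between two primary models would be made with the outcome data in hand.

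**Working it through.** **Inputs.** Means 7 and 10, SD 3.3 in both arms, 33 per arm, 95% power (SAP 4); two-sided 0.05 (SAP 6.1); 1:1 allocation (SAP Study Design). Assumptions not stated in the documents: model-based standard error with the scale fixed at 1 (the natural reading of SAP 6.1 and 8.1), equal full follow-up, no covariates.

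**1. The plan's own figure.** For a two-sided two-sample t-test with difference 3 and SD 3.3, exact power is 94.7% at 32 per arm and 95.3% at 33. The stated 33 is reproduced, so 3.3 is the SD on which the stated power rests.

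**2. Variance assumed against variance modelled.** The planning variance is 3.3² = 10.89.

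| Mean | Poisson SD = √mean | Dispersion = 10.89/mean |
|---|---|---|
| 7 | 2.65 | 1.56 |
| 8.5 | 2.92 | 1.28 |
| 10 | 3.16 | 1.09 |

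**3. Type I error.** With a common mean in both arms, the Poisson Wald test has error 2 × [1 − Φ(1.96/√dispersion)].

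- Mean 7: 1.96/1.247 = 1.571, giving 11.6%.
- Mean 8.5: 1.96/1.132 = 1.732, giving 8.3%.
- Mean 10: 1.96/1.044 = 1.878, giving 6.0%.

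Simulation with 100,000 trials per setting (33 and 40 per arm; negative binomial counts, and beta-binomial counts with an assumed ceiling of 13) gave 11.4–11.6%, 8.4–8.5% and 5.9–6.2%.

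**4. Interval at the planned effect (7 versus 10, 33 per arm).**

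- Poisson SE of the log rate ratio: √[1/(33×7) + 1/(33×10)] = 0.0858.
- SE with SD 3.3: √[(10.89/33) × (1/49 + 1/100)] = 0.1002.
- Ratio: 0.1002/0.0858 = 1.17.
- Coverage of the nominal 95% interval: 2Φ(1.96/1.168) − 1 = 90.7%.
- The rate ratio is 10/7 = 1.43, with log 0.357. The Poisson interval is exp(0.357 ± 1.96×0.0858) = 1.21 to 1.69. The interval that matches SD 3.3 is exp(0.357 ± 1.96×0.1002) = 1.17 to 1.74.

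**5. Dependence on the SD.** Type I error from the formula in step 3:

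| True SD | Mean 7 | Mean 8.5 | Mean 10 |
|---|---|---|---|
| 3.3 | 11.6% | 8.3% | 6.0% |
| 3.0 | 8.4% | 5.7% | 3.9% |
| 2.65 | 5.0% | 3.1% | 1.9% |
| 2.0 | 1.0% | 0.4% | 0.2% |

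The test is anti-conservative when the SD exceeds the Poisson value and conservative when it falls below it.

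**6. Would the planned check catch it?** The SAP names no test. As an illustration, a Pearson dispersion test at the 5% level, with SD 3.3, detects the overdispersion in about 80–92% of trials at common mean 7, 43–51% at 8.5, 13–21% at 10, and 49–59% at 7 versus 10. If a positive result always triggered the negative binomial model, type I error would be about 5.3–6.4%.

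**7. Alternatives at SD 3.3.**

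- Log-link Poisson model with robust standard errors: type I error about 5.4–5.8% at 33 per arm, the lower end with an n/(n−1) correction.
- Negative binomial in every case: about 4.7–5.5%.
- Unequal-variance t-test, standing in for the bootstrap t-test: about 5.0%.
- Analytic power for the robust analysis at 33 per arm: Φ(0.3567/0.1002 − 1.96) = Φ(1.60) = 94.5%; the same calculation at 40 gives 97.5%.

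**The case against.** **The SD is only a planning input.** This stands. A reader might infer that the primary interval is too narrow and that type I error exceeds 5% as a matter of fact. The documents do not support that. They give 3.3 as an assumption in a two-mean calculation, not as a measured property of the outcome, and step 5 shows that a smaller SD reverses the direction. Underdispersion is plausible because a woman can have only so many cycles in a year. The documents state no ceiling, however, and protocol 4.3 admits women with cycles shorter than 21 days, so a limit of 13 is an assumption.

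**The mismatch is uneven.** This also stands. At mean 10 the planning SD is close to Poisson (3.3 against 3.16), and the error rate there is 6.0%. Most of the problem lies in the medical care arm.

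**The SAP has other safeguards.** A reader might infer that the optional switch is all the plan offers. That is not so: overdispersion testing and the bootstrap t-test are both firm commitments, and the t-test does not rely on Poisson variance. A disagreement between it and the primary result would be visible. But the test for overdispersion has no stated consequence, and the t-test is a sensitivity analysis on the difference scale, restricted to women with complete follow-up. It cannot correct the primary p-value or the rate-ratio interval.

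**A binding switch would nearly suffice.** On the planning SD it would (5.3–6.4%), but the SAP does not commit to one. The negative binomial model also cannot represent underdispersion, so a switch to it helps in one direction only.

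**At the planned effect the conclusion would not change.** True: both intervals in step 4 exclude 1. The error rate matters when the effect is absent or small.

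**Conclusion.** The concern holds conditionally. The SAP sizes the trial on one variance and tests on a smaller one. If SD 3.3 is right, the true standard error at 7 versus 10 is 1.17 times the Poisson one, the 95% interval covers about 91%, and type I error is about 6–12% depending on the common mean. This rests on a model-based standard error with scale fixed at 1, equal follow-up and no covariates. If counts are underdispersed, the same test is conservative and loses efficiency instead.

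In either case the calibration of the primary test depends on an unverified variance assumption, and the only remedy for the primary estimate is optional, has no threshold and works in one direction.

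A reader might also infer that the sample size is wrong. It is not: 33 per arm is correct for the stated inputs.

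**What to change.** In SAP 6.1 and 8.1, define the primary analysis as the log-link Poisson model with robust (sandwich) standard errors, preferably with a named small-sample correction, and delete the data-dependent switch. Report the negative binomial model and the bootstrap t-test as sensitivity analyses in every case, whatever the dispersion. Apply the same wording to reported menses in 8.2.

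Robust standard errors respond to the observed spread in both directions, so no threshold is needed, and the rate ratio remains the reported effect.

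The cost is one or two sentences in the SAP and one setting in the software. On the planning figures at 33 per arm the interval widens from about 1.21–1.69 to about 1.17–1.74. Type I error is about 5.4–5.8%, still slightly above nominal, which is why a small-sample correction is preferable. Power is about 94.5–95%, in line with the stated 95%. Using the negative binomial model in every case would also control the error under overdispersion, but it offers nothing if the counts are underdispersed.
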